Aim 3: Evaluate facilitators of and barriers to scalability, acceptability, and sustainability of financial incentives plus tailored messages based on SDT principles, financial incentives, and tailored messages based on SDT principles. To identify facilitators of and barriers to intervention implementation and sustainability, we will interview participants, workplace health promotion staff, and health system staff. With these interview data and program cost data, we will evaluate program implementation and sustainability using an integration of the Reach, Effectiveness, Adoption, Implementation, and Maintenance and Consolidated Framework for Implementation Research frameworks.

Aim 4: Compare 12-month changes in HbA1c and weight in the Enhanced Usual Care (EUC) arm to similar patients who received no intervention. This exploratory aim was added after analyses of primary and secondary outcomes found that participants in the least research-intensive arm, the Enhanced Usual Care (EUC) arm, saw the best improvements in weight and HbA1c. We will conduct an analysis to compare the HbA1c and weight outcomes in the EUC arm to similar patients who received no intervention (external controls). The results will be used to provide context to staff who we interview as part of Aim 3.

Background Information

Significance

Prediabetes Is a Major Public Health Problem in the United States. Prediabetes is an asymptomatic condition in which patients' blood glucose levels are higher than normal but not high enough to meet diagnostic criteria for type 2 diabetes mellitus (T2DM). The American Diabetes Association (ADA) defines prediabetes as either a fasting plasma glucose (FPG) of 100 to 125 mg/dL, a 2-hour plasma glucose of 149 to 199 mg/dL after a 75-gram oral glucose tolerance test, or a hemoglobin A1c (HbA1c) of 5.7% to 6.4%. An estimated 84 million US adults have prediabetes, which is associated with an approximately 3-fold greater annual incidence of T2DM and an approximately 50% greater risk of consequent cardiovascular disease.

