Overview. To test our novel strategy of linking financial incentives and preventing T2DM to people's roles, values, and strengths, our team of experts in T2DM prevention, behavioral economics, and SDT will conduct a 4-arm pragmatic RCT among patients of Michigan Medicine (the U-M health system) who have prediabetes and U-M Premier Care health insurance. Our study will utilize the Way to Health (W2H) web platform of the University of Pennsylvania (Penn). This platform was developed with support from NIH and permits automated delivery and efficient evaluation of behavioral interventions that leverage insights from behavioral economics. We will compare the effects of 12 months of (a) financial incentives plus tailored messages based on SDT principles, (b) financial incentives alone, (c) tailored messages based on SDT principles alone, and (d) an enhanced control group on the primary outcome of change in HbA1c. These four arms will enable evaluations of the effects of adding tailored messages to financial incentives (i.e., financial incentives plus tailored messages vs. financial incentives alone), adding financial incentives to tailored messages (i.e., financial incentives plus tailored messages vs. tailored messages alone), and adding both tailored messages and financial incentives to automated feedback (i.e., financial incentives plus tailored messages vs. enhanced control). To measure the primary outcome of change in HbA1c, and secondary outcome of change in weight, we will conduct assessments at baseline, 6, and 12 months. To measure the secondary outcome of participation in a DPP or use of metformin we will use health insurance claims data. We will measure mediators and moderators of intervention effectiveness by surveying participants at baseline, 6, and 12 months. To identify facilitators of and barriers to intervention implementation and sustainability, after the 12-month intervention we will interview participants, workplace health promotion staff, and PCPs. We will then conduct a comprehensive evaluation of program implementation and sustainability using the Reach, Effectiveness, Adoption, Implementation, and Maintenance (RE-AIM) and Consolidated Framework for Implementation Research (CFIR) frameworks.

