Measures taken to protect privacy and confidentiality are described in the *Privacy and Confidentiality Measures* section of this protocol.

Strategies to Maximize Retention and Data Collection. Participants will receive \$50 when they complete each assessment consisting of the online survey, weigh-in, and A1c test. They will also receive email, text messages, and phone calls to remind them to complete these tasks. We used this approach to limit attrition rates to 2% at 12 weeks in our pilot study and to less than 10% at nine months in two previous trials.^{39,41}

Statistical Design

Sample Size

Based on data from previous studies, in the Enhanced Control Arm we anticipate a mean 12-month absolute HbA1c change (defined as the 12-month measure minus the baseline measure) of 0.0%, a mean 12-month absolute HbA1c decrease of 0.2% in both the Financial Incentives Arm and the Tailored Messages Arm, and a mean 12-month absolute HbA1c decrease of 0.4%

in the Combo Arm. Assuming a 0.4% standard deviation for 12-month HbA1c change in each arm and using an α of 0.017 to adjust for three main comparisons, 85 subjects per arm will provide 99% power to detect the difference between the Financial Incentives Plus Tailored Messages and Enhanced Control Arms (H1a), and 80% power to detect differences between the Combo Arm and the Tailored Messages Arm and the Financial Incentives Arm (H1b). With this sample size, we will also be able to detect meaningful differences (Cohen's d of 0.5 or larger) in secondary outcomes of weight, months of engagement in a Diabetes Prevention Program (DPP), months of taking metformin, and months of engagement in a DPP or taking metformin. To account for possible attrition we have conservatively inflated our sample size by 10% and will enroll 380 participants.

Analysis Plans

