Our primary analytic approach will use ordinary least squares (OLS) regression models for continuous outcomes, adjusting for two stratification variables used in randomization (household income and autonomous motivation to prevent diabetes). To assess balance in randomization, we will compare baseline survey measures across arms. Additionally, we expect some missing data on baseline measures and outcomes and will assess the extent and pattern of missingness (e.g., monotone missingness) and predictors of missing outcomes. If we find a baseline measure to be predictive of missing outcome data, we will also adjust for this measure in analyses of outcomes. As an alternative analytic strategy, we will also use mixed-effects models. We will assess for consistency in the results between the two analytic approaches. If more than 10% of the 12-month data are missing, we will also use a multiple imputation strategy in which we will generate ten imputed datasets for missing data using a sequential regression multivariable imputation method, including intervention arms and other baseline variables.¹⁸⁵ The estimates from both the OLS and mixed-effects model analyses using imputed datasets will then be combined using the method of Rubin and Little.¹⁸⁶ All analyses of outcomes will use an intent-to-treat approach and a Bonferroni corrected α of 0.017. Data will be analyzed by a Data Analyst who will be blinded to arm assignment until all primary outcome data have been collected.

Aim 1: Compare the effectiveness of financial incentives plus tailored messages based on SDT principles, financial incentives, and tailored messages based on SDT principles in decreasing hemoglobin A1c, and weight, and in increasing participation in a DPP or use of metformin.

H1a: The mean decrease in HbA1c will be greater in the Combo Arm than in the Enhanced Control Arm.

H1b: The mean decrease in HbA1c will be greater in the Combo Arm than in the Financial Incentives Arm and the Tailored Messages Arm.

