Mean 12-month change in HbA1c (defined as the 12-month measure minus the baseline measure) will be reported by arm. To test H1a and H1b, we will use an OLS regression model with 12-month change in HbA1c as the response variable. This model will include an indicator for each of the three arms (with the Financial Incentives Plus Tailored Messages Arm as the reference), stratification factors, baseline HbA1c values, and any baseline measures that are predictive of missing 12-month data. We will use similar, separate OLS regression models to predict our secondary outcomes of 12-month changes in weight (defined as the difference between the 12-month and baseline measures) and mean number of months (calculated out of 12 months to account for those who drop out before 12 months) in which individuals were engaged in a DPP, mean months in which individuals had a metformin PDC of at least 0.8, and mean months in which individuals were engaged in a DPP or had a metformin PDC of at least 0.8.

In alternate analyses, we will fit separate mixed-effects models for the primary and secondary outcomes using baseline, 6, and 12-month data as response variables and with time, study arm indicators, and interactions between time and study arm indicators as predictors and participants as random intercepts. We expect the changes in outcomes in intervention arms to be gradual over time and anticipate these longitudinal data models will confirm findings from our primary analytic approach to testing H1a and H1b, but if the findings differ, we will examine the source of any differences. For models for months of engagement in a DPP or use of metformin, we will first assess the distribution for skewness and, if more appropriate, a count data model (e.g., zero-inflated negative binomial) will be used instead of OLS.

Aim 2: Identify mediators and moderators of the effectiveness of financial incentives plus tailored messages based on SDT principles, financial incentives, and tailored messages based on SDT principles.

H2a: Combo Arm on 12-month change in HbA1c will be mediated by changes in autonomous motivation and changes in controlled motivation.

H2b: Effects of the Financial Incentives Arm on 12-month change in HbA1c will be mediated by changes in controlled motivation.

H2c: Effects of the Tailored Messages Arm on 12-month change in HbA1c will be mediated by changes in autonomous motivation.

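### Does the 80% power quoted for H1b overstate the chance of showing that the Combo Arm beats both single-component arms?

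*Combined protocol and SAP*

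**What the plan says.** The Sample Size section assumes a mean 12-month HbA1c change of 0.0% in the Enhanced Control Arm, decreases of 0.2% in each single-component arm, and a decrease of 0.4% in the Combo Arm. The spread is given by "Assuming a 0.4% standard deviation for 12-month HbA1c change in each arm". The significance level is set "using an α of 0.017 to adjust for three main comparisons". With 85 per arm the section claims 99% power for H1a (Combo against control) and "80% power to detect differences between the Combo Arm and the Tailored Messages Arm and the Financial Incentives Arm (H1b").

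Analysis Plans, Aim 1, words H1b as "The mean decrease in HbA1c will be greater in the Combo Arm than in the Financial Incentives Arm and the Tailored Messages Arm". The same section states: "All analyses of outcomes will use an intent-to-treat approach and a Bonferroni corrected α of 0.017". The primary model is a single regression of 12-month change with "an indicator for each of the three arms (with the Financial Incentives Plus Tailored Messages Arm as the reference), stratification factors, baseline HbA1c values". Further covariates enter if they turn out to predict missingness.

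The Overview under Approach describes what the four arms are for. Its list begins with "evaluations of the effects of adding tailored messages to financial incentives (i.e., financial incentives plus tailored messages vs. financial incentives alone") and continues, as separate items, with Combo against tailored messages alone and Combo against the enhanced control.

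**The concern.** H1b joins two comparator arms with 'and', and the Sample Size section attaches one power figure to that label. Read literally, H1b holds only if the Combo Arm is better than both arms, and the power to establish that is lower than the power of either comparison alone. If 80% is only the single-comparison figure, the chance of failing to establish H1b under the sponsor's own assumptions is about 31% (100 − 69), not the 20% a reader would infer.

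Two things would be at stake. A trial in which exactly one of the two comparisons is significant is a fairly likely outcome, and the plan does not say what H1b is then called. A reader might also make too much of an unsupported H1b, believing the trial had 80% power for it. The validity of the tests was never in question.

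**Working it through.** **Inputs** (Sample Size, except where noted): n = 85 per arm; difference between Combo and each single-component arm = 0.4 − 0.2 = 0.2; SD = 0.4; α = 0.017. Allocation is equal (Randomization). Sidedness is not stated.

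**1. Reproduce the 80%.** Noncentrality for one comparison is δ / (σ√(2/n)) = 0.2 / (0.4 × √(2/85)) = 3.260.

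- Two-sided critical value (normal): z = 2.387. Power = Φ(3.260 − 2.387) = Φ(0.873) = 0.809.
- Noncentral t: 0.801 on 168 df; 0.805 with the variance pooled over four arms (336 df).
- One-sided at 0.017, the power would be about 0.87. The stated 80% therefore points to two-sided testing, which is assumed below.

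The figure reproduces as the power of a single comparison. For H1a the difference is 0.4 and power exceeds 0.999, so the stated 99% is conservative.

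**2. Power for both comparisons.** The two test statistics share the Combo Arm. With equal arms their correlation is (σ²/n) / (2σ²/n) = 0.5. The probability that both exceed the critical value is the bivariate normal Φ₂(0.873, 0.873; ρ = 0.5) = 0.699. Simulation of the pooled-variance t tests gives 0.694 to 0.695, so about 69%.

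**3. At least one, and exactly one** (normal approximation).

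- At least one: 2 × 0.809 − 0.699 = 0.918 by the normal formula; 0.915 by simulation with t tests.
- Exactly one: 2 × (0.809 − 0.699) = 0.22.

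**4. How far the 69% depends on its premises.**

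| Setting | Power for both |
|---|---|
| 85 per arm, α 0.017, unadjusted | 0.69 |
| 85 per arm, α 0.025 (α split over two hypotheses only) | 0.75 |
| 95 per arm (all 380 analysed), α 0.017 | 0.76 |
| 85 per arm, covariates explain an assumed 10% of variance | 0.76 |
| 85 per arm, covariates explain an assumed 20% of variance | 0.82 |

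Unadjusted, 80% for both needs about 102 analysable per arm. Equivalently, at 85 per arm the covariates must explain 1 − 85/102 = 0.167, about 17% of the variance. The planned model does adjust for baseline HbA1c and the stratification factors, but the documents give no R², so the adjusted figure is unknown.

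**5. Which reading the text supports.**

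- The α of 0.017 is 0.05/3. H1a is one comparison, so a count of three is reached only if H1b is counted as two.
- The power sentence uses the singular for H1a and the plural 'differences' for H1b.
- The Overview lists the three contrasts as separate evaluations, each answering its own question.
- With the Combo Arm as reference, the model yields one coefficient and one test per comparison. No joint or both-must-succeed test is defined anywhere.

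Against these stands only the word 'and' in H1b, which is ordinary shorthand for two pairwise statements about means.

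**The case for a change.** The strongest case for acting is that the arithmetic is right and a clarification costs almost nothing. No sentence labels the 80% as per comparison. H1b as worded is a conjunction, its unadjusted power is about 69%, and even analysing all 95 per arm or relaxing α to 0.025 leaves it below 80%. About 22% of trials run under the plan's assumptions would end with exactly one of the two comparisons significant, and a plan that does not say how H1b is then described leaves some latitude in the write-up.

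The figures stand, and so does the missing label. The step to a defect does not. The 69% takes its success criterion from an all-or-nothing H1b but its α from a three-comparison plan. If H1b were one hypothesis requiring both tests to succeed, its components would need no α division between them, and a consistent split with H1a gives 75%. That is before any gain from the planned baseline adjustment. The latitude in reporting is also small: the planned model already produces both comparisons separately, each judged at 0.017, so a mixed result is visible as such whatever H1b is called.

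**Conclusion.** No change to the plan is needed. The 80% is a correct power for each Combo-versus-single-arm comparison, and that is the reading the α allocation, the Overview and the model all support. What is missing is a label that a statistician supplies without difficulty. A reader who wants the joint figure can take it as about 69% with 85 per arm, unadjusted, rising to about 80% if covariates explained some 17% of the variance.

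These figures rest on the plan's own means and SD, on two-sided testing (assumed because it reproduces the 80%), and on assumed values for variance explained.

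Following the plan as written gives valid tests at the stated error rate and a separate result for each comparison. Restating the design-stage power would change none of that. Declaring H1b supported only when both comparisons are significant would be a new decision rule resting on one conjunction. It would also come too late to count as prespecified, since the text of Aim 4 records: "This exploratory aim was added after analyses of primary and secondary outcomes found that participants in the least research-intensive arm" did best on weight and HbA1c.

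### Ten imputations leave avoidable seed noise in a supplementary analysis read against 0.017; a larger number with a fixed seed is a free, minor improvement

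*Combined protocol and SAP*

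**What the plan says.** All of this is in the combined protocol and SAP, Statistical Design.

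- **Primary analysis (Analysis Plans).** "Our primary analytic approach will use ordinary least squares (OLS) regression models for continuous outcomes". The model given for H1a and H1b under Aim 1 mentions no imputation.
- **Trigger and role.** "If more than 10% of the 12-month data are missing, we will also use a multiple imputation strategy". Imputation is therefore conditional and comes on top of the OLS and mixed-effects analyses.
- **Number and method.** "we will generate ten imputed datasets for missing data using a sequential regression multivariable imputation method", with the imputation model described as "including intervention arms and other baseline variables". The OLS and mixed-model estimates from the imputed data are then "combined using the method of Rubin and Little".
- **Threshold.** "All analyses of outcomes will use an intent-to-treat approach and a Bonferroni corrected α of 0.017". This covers the imputed analyses as well.
- **Attrition (Sample Size).** The trial is powered on 85 per arm and enrols 380.

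The documents give no reason for ten, no random seed and no check of Monte Carlo error.

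**The concern.** A pooled estimate from m imputed datasets carries simulation noise that depends on the seed and shrinks as m grows. Imputation is used here only once more than 10% of 12-month data are missing, so the noise is not negligible when m is ten. Someone who re-runs the same analysis on the same data with another seed gets a somewhat different p-value. If the imputed result lies near 0.017, the seed can decide which side it falls on.

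What is at stake is the reading of the supplementary analysis. When imputed and non-imputed results differ, the difference should tell the reader about the missing data. With ten datasets, part of it may be chance in the imputation draws. H1b is planned at only 80% power, so an H1b result near the threshold is realistic.

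**Working it through.** **1. The plan's own figures.** Inputs from Sample Size: 85 per arm, SD of change 0.4, "using an α of 0.017 to adjust for three main comparisons", and "a mean 12-month absolute HbA1c decrease of 0.2% in both the Financial Incentives Arm and the Tailored Messages Arm" against decreases of 0.4 in the Combo Arm and 0.0 in the Enhanced Control Arm. Sidedness is not stated; two-sided is assumed, giving z = 2.387.

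- SE of a difference = 0.4 × √(2/85) = 0.0614.
- H1b: 0.2/0.0614 = 3.26; Φ(3.26 − 2.387) = 80.9% (80.1% with the noncentral t). Stated: 80%.
- H1a: 0.4/0.0614 = 6.52; power above 99.9%. Stated: 99%.
- Enrolment: 340/0.9 = 378, or 340 × 1.1 = 374. Stated: 380.

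These reproduce adequately.

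**2. Would imputation be triggered?** (380 − 340)/380 = 40/380 = 10.5%, which is above 10%. Attrition down to the powered number is enough.

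**3. Size of the seed noise.** Let FMI be the fraction of missing information. The Monte Carlo SD of the pooled estimate, in units of its standard error, is about √(FMI/m).

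- m = 10: √(0.10/10) = 0.100; √(0.20/10) = 0.141.
- m = 100: √(0.10/100) = 0.032; √(0.20/100) = 0.045.

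FMI is an assumption. In simulation with arm and a baseline covariate as the only predictors, it was close to the missing rate: 0.11–0.12 at 11% missing and 0.20–0.21 at 20%. The plan does not list 6-month HbA1c in the imputation model; including it could lower the FMI.

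For a result that would be p = 0.017 with unlimited imputations, the estimate's noise alone at FMI 0.10 and m = 10 gives z = 2.387 ± 1.96 × 0.100 = 2.191 to 2.583, or p about 0.028 to 0.010. Adding the noise in the between-imputation variance (Rubin pooling with Barnard–Rubin degrees of freedom) widens this. The 95% ranges across seeds are:

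| FMI | m = 10 | m = 50 | m = 100 |
|---|---|---|---|
| 0.10 | 0.009–0.032 | 0.013–0.022 | 0.014–0.021 |
| 0.20 | 0.007–0.047 | 0.011–0.026 | 0.013–0.023 |

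The effect is not limited to a value exactly at the threshold. With m = 10, a p-value that would be 0.013 falls below 0.017 in 76% of seeds at FMI 0.10 and 62% at 0.20. With m = 100 this is nearly 100% and 95%.

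**4. How often it matters under the design assumptions.** Four arms of 95, mean changes −0.4, 0, −0.2 and −0.2, SD 0.4, data missing completely at random, imputation from arm and a baseline covariate, two independent seeds per dataset, 1,500 datasets per setting. The table shows how often the two seeds disagree at 0.017, averaged over the two H1b comparisons:

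| Missing | m = 10 | m = 50 | m = 100 |
|---|---|---|---|
| 11% | 3.8% | 1.7% | 0.8% |
| 15% | 5.8% | 2.7% | 2.1% |
| 20% | 7.8% | 3.5% | 2.1% |
| 30% | 11.5% | 4.7% | 3.3% |

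For one comparison at a 4% rate, the simulation error is √(0.04 × 0.96/1500) = 0.5 percentage points. For H1a, disagreement was at most 0.1% at every m.

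**The case against.** The strongest reply is that no stated decision rests on the imputed p-value. A reader might infer that the confirmatory tests of H1a and H1b are unstable. The documents do not support that: those tests are OLS models without imputation, and the imputed analysis is conditional and additional. This stands in full.

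A reader might also take imputation to be the plan's main safeguard against dropout. The documents do not rank it so. They also plan to examine the pattern and predictors of missingness, to adjust for baseline predictors of missing outcomes, and to fit mixed-effects models to the baseline, 6- and 12-month data. This stands too.

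Nor are ten imputations invalid. By Rubin's formula the relative efficiency, 1/(1 + FMI/m), is 1/(1 + 0.10/10) = 0.99 at FMI 0.10 and 1/(1 + 0.20/10) = 0.98 at 0.20. The loss is in reproducibility of the p-value near the threshold.

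More datasets narrow the unstable zone without removing it. A result exactly at 0.017 falls below it in 45% of seeds with ten datasets and 48% with 100 (FMI 0.10). Clear results were already safe: a p-value of 0.005 stays below 0.017 in at least 97% of seeds up to FMI 0.20, even with ten.

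Finally, the change comes late. Aim 4 (Specific Aims) was added after primary and secondary outcomes had been analysed. That affects how the change must be reported, but the noise remains.

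**Conclusion.** The point holds as a minor, free improvement. With ten datasets, an imputed H1b conclusion at 0.017 would differ between two seeds about 4–8% of the time at 11–20% missing, against about 1–2% with 100. H1a is essentially unaffected. The primary OLS test and the stated power, α and sample size are untouched.

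The sizes rest on an FMI near the missing rate, data missing completely at random, two-sided testing and the plan's own effect sizes and SD. A lower FMI would shrink the noise. The documents report neither the actual missing rate nor any p-value, so they do not show whether imputation was run or whether any result was borderline.

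**What to change.** In Analysis Plans, replace ten with at least 50 imputed datasets, for example 100. Fifty captures much of the gain; 100 brings two-seed disagreement on H1b to about 2% or less at up to 20% missing. Fix the random seed and report it, and report the Monte Carlo error of the pooled estimates and p-values.

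If an imputed Aim 1 analysis has already been run with ten datasets, re-run it with the larger number and state that the change was made after the initial analysis.

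The cost is computing time and a sentence of disclosure. No design feature, data collection or primary analysis changes.

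### Does the conditional multiple imputation need to name 6-month HbA1c as a predictor?

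*Combined protocol and SAP*

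**What the plan says.** The primary analysis is an OLS regression of 12-month HbA1c change on arm, stratification factors, baseline HbA1c and any baseline measure that predicts missing 12-month data (Analysis Plans, Aim 1). The analysts will "assess the extent and pattern of missingness (e.g., monotone missingness) and predictors of missing outcomes".

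Imputation is conditional and additional: "If more than 10% of the 12-month data are missing, we will also use a multiple imputation strategy". Its content is to "generate ten imputed datasets for missing data using a sequential regression multivariable imputation method, including intervention arms and other baseline variables". The imputed datasets serve two models: "The estimates from both the OLS and mixed-effects model analyses using imputed datasets will then be combined".

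The alternate mixed-effects models are fitted whether or not imputation is triggered, "using baseline, 6, and 12-month data as response variables". On disagreement with OLS the plan says "if the findings differ, we will examine the source of any differences".

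On expected losses, the retention paragraph says that the team's approach served to "limit attrition rates to 2% at 12 weeks in our pilot study and to less than 10% at nine months in two previous trials". The Sample Size section says the team "conservatively inflated our sample size by 10% and will enroll 380 participants".

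**The concern.** Arm and baseline HbA1c are already in the OLS model. Imputing the missing outcome from the same variables brings in no new information, so the result should sit almost on top of the complete-case estimate. If people leave because their 6-month result was poor, and do so more in one arm, neither analysis corrects for it. Imputed OLS and imputed mixed-model results could then agree with each other and with complete case while all three share one bias. The 6-month value that could repair this is measured and costs nothing extra. An imputation step kept for the case of heavier dropout should use it, and the text does not say that it will.

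**Working it through.** **1. The plan's own figures.** Enrolment: 85 / (1 − 0.10) = 94.4, rounded up to 95 per arm; 4 × 95 = 380. The reserve is (380 − 340) / 380 = 10.5%. Power for a difference of 0.2 with SD 0.4, 85 per arm and α = 0.017 (two-sided assumed; the plan does not say) is 80.9% by the normal formula and 80.1% by the noncentral t, against the stated 80%.

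**2. Would the trigger be met?** It needs more than 0.10 × 380 = 38 missing. Carrying the plan's attrition figures forward at a constant rate (assumption):
- from 2% at 12 weeks: 1 − 0.98^(52/12) = 8.4% at one year;
- from the 10% ceiling at nine months: 1 − 0.90^(12/9) = 13.1% at most.

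The range straddles the trigger, so whether it is met is open.

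**3. What the method would do.** Three features of the text point the same way.
- The list is introduced by *including*, which does not close it.
- The imputed datasets must support a mixed model with 6-month HbA1c among its responses, so that variable has to be in them.
- Sequential regression conditions each incomplete variable on the others. The default routine in statsmodels, given arm, baseline, 6- and 12-month HbA1c, uses `y12 ~ arm + b + y6`.

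**4. Size of the bias if 6-month HbA1c were left out.** Simulation inputs: two arms of 95, true difference −0.20, SD 0.4 (Sample Size section). Assumed: correlation of 6- and 12-month change 0.5 or 0.7; dropout tied to poor 6-month response in the Combo Arm only, odds 2.5 per SD; every dropout has a 6-month value. There were 1,500 replicates and ten imputations, with Monte Carlo SE 0.0007 or less. Entries are bias in HbA1c points at correlation 0.5 / 0.7.

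| Analysis | 10.5% missing | 12% missing | 13.1% missing |
|---|---|---|---|
| Complete-case OLS | −0.0187 / −0.0245 | −0.0201 / −0.0286 | −0.0223 / −0.0307 |
| Imputation from arm and baseline HbA1c, then OLS | −0.0187 / −0.0244 | −0.0201 / −0.0284 | −0.0225 / −0.0309 |
| Same imputation, then mixed model | −0.0186 / −0.0244 | −0.0201 / −0.0284 | −0.0224 / −0.0310 |
| Mixed model on observed data (planned) | −0.0070 / −0.0122 | −0.0070 / −0.0143 | −0.0081 / −0.0151 |
| Imputation adding 6-month HbA1c | −0.0012 / −0.0003 | −0.0003 / +0.0001 | −0.0006 / +0.0001 |

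The standard error is about 0.062 (check: 0.4 × √(2/85) = 0.061). The largest bias is 0.031 / 0.062 = 0.50 SE. At odds 1.5 the bias with arm-and-baseline imputation is 0.0082 to 0.0149; the smallest is 0.0082 / 0.062 = 0.13 SE.

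**5. Gain over what is already planned.** The planned observed-data mixed model less imputation with 6-month HbA1c runs from 0.0070 − 0.0012 = 0.0058 to 0.0151 − 0.0001 = 0.0150, or 0.09 to 0.24 SE.

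**6. How far the result depends on the assumptions.**
- Same dropout rule in both arms: bias 0.0056 or less with arm-and-baseline imputation.
- Half the dropouts without a 6-month value (odds 2.5, 10.5% missing): adding 6-month HbA1c only moves the bias from −0.0181 / −0.0251 to −0.0084 / −0.0114.
- No dropout with a 6-month value (a separate run at 20% missing, correlation 0.5): −0.045 with or without it.
- One further informative baseline variable in the imputation (13.1% missing, 6-/12-month correlation 0.6): complete-case bias of about −0.029 becomes −0.025 if that variable correlates 0.3 with change, and −0.018 if 0.5. The plan's list does contain other baseline variables.

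**7. Precision under purely random dropout.** Large-sample variance relative to complete case, with 6-month HbA1c used, is 1 − (missing share) × (correlation)². At 10.5%: 1 − 0.105 × 0.25 = 0.974 and 1 − 0.105 × 0.49 = 0.949. At 13.1%: 0.967 and 0.936. Simulation gave 0.978 / 0.951 and 0.979 / 0.936. Arm-and-baseline imputation gave 1.010 to 1.018.

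**The case for a change.** The best case for acting is that the text allows two imputation models that behave differently, and one clause would settle it. The stated remedy for predictors of missingness covers only baseline measures, so a 6-month response that predicts dropout has no named remedy in the OLS or imputation steps. The random-intercept mixed model helps but leaves 0.007 to 0.015 at odds 2.5. Losses could also exceed the reserve. At 20% missing, with log-odds of 1 per SD in the Combo Arm and all 6-month values present, arm-and-baseline imputation is biased by 0.023 to 0.054 for correlations 0.3 to 0.7. The upper end is 0.054 / 0.066 = 0.8 SE.

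The arithmetic stands. So does one caution on interpretation: if 6-month HbA1c was in fact left out, agreement between the two imputed analyses says little about whether dropout did harm. The step from there to a change in the plan does not stand. It needs an analyst to remove a variable that the method and the second model would bring in, and then one-sided dropout tied to that variable. The monthly engagement and prescription feeds were also suggested as auxiliary predictors, but no gain from them was shown. Nor would an edit now be free. Aim 4 records that the primary and secondary outcomes had been analysed before this version, so a new imputation rule would be written with the arm results known.

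**Conclusion.** No change to the plan. The wording leaves a detail open, and the named method, run on data that must also serve the mixed model, normally fills it with 6-month HbA1c. If that variable were deliberately left out and the other baseline variables were weak predictors, the imputation would nearly repeat complete case. Bias of about 0.01 to 0.03 HbA1c points at 10.5% to 13.1% missing would further need dropout that depends on 6-month response differently by arm. The documents neither show nor exclude such dropout. The correlations, the dropout rule and the attrition extrapolation are assumptions; the 95 per arm, the SD of 0.4 and the 10% trigger are the plan's. The analysis affected is conditional and supplementary. The primary OLS model, the alpha, the sample size and the observed-data mixed model do not depend on it. Which variables entered the imputation, if it was run, is ordinary detail for the report of results.
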